3.10 Supplementary and Sensitivity Analyses for Primary and Secondary Endpoints

The following are supplementary and sensitivity analyses for the primary and secondary endpoints:

- The primary and secondary efficacy endpoints will be performed on the mITT population.
- The htTKV at Months 18, 24, and 30 days post-dose will be analyzed in the manner as described in Section 3.9.2.
- A longitudinal analysis of htTKV (as described in Section 3.10.1)
- A longitudinal analysis of eGFR (as described in Section 3.10.23.10.1)

3.10.1 htTKV Longitudinal Analysis

An MMRM analysis will be performed on the htTKV data. The following is the MMRM model:

$$Y_{ij} = \beta_1 + \beta_2 \times Group_i + \beta_3 \times t_{ij} + \beta_4 \times t_{ij} \times Group_i + b_{1i} + b_{2i} \times t_{ij} + e_{ij}$$

Where:

Y_{ij}	is the $\log_{10}(hTKV)$ values for subject i at visit j (ie, at baseline; months 12, 18, and 24; and 30-days post-dose)
$Group_i$	is the treatment group indicator for Subject i (=0 if placebo, =1 if KD019)
t _{ij}	is the time (in years) from baseline of the htTKV assessment
β_{I}	is the intercept for the placebo group
β_2	is the intercept increment for the KD019 group (ie, $\beta_1 + \beta_2$ is the intercept for the KD019 group)
β_3	is the slope for the placebo group
eta_4	is the slope increment for the KD019 group (ie, $\beta_2 + \beta_4$ is the slope for the KD019 group)
b_{li}	Is the random intercept term for subject i
b_{2i}	Is the random slope term for subject i
e _{ij}	Is the error term for subject i , visit j .

Note: the random effects, b_{1i} and b_{2i} are assumed to be normally distributed with mean 0 and unknown variance covariance structure (ie, an unstructured 2×2 covariance matrix will be modelled). The error terms in the model, e_{ij} , are assumed mutually independent and normally distributed; and they are also assumed to be independent of the random effects, b_{1i} and b_{2i} .

This model will test for a difference in slopes between placebo and KD019 (ie, testing the fixed effect parameter β_4).

The following is the corresponding sample SAS Proc Mixed code for this MMRM model:

Table 2: Sample SAS Code of Longitudinal MMRM Analyses

```
** Sample SAS Code for MMRM **;
Proc Mixed Data=XXX;
Class Trt subject;
Model log_htTKV = treatment time treatment*time/s
Random intercept time / type=un subj=subject;
Run;
```

3.10.2 eGFR Longitudinal Analysis

The slope of eGFR change will be analyzed by an MMRM analysis.

The MMRM model will be the same as the model described in Section 3.10.1 with the dependent variable being the subjects eGFR values. The model will include the baseline and all post-baseline eGFR assessments.

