3.9.2 Primary Endpoint Analysis

The primary efficacy endpoint is the change from baseline in htTKV at Month 12. An ANCOVA model including treatment group as a factor and the baseline htTKV (log_{10} transformed) as a covariate will be used for efficacy analyses. The dependent variable is the log10 transformed change from baseline (ie, log_{10} (Month 12 htTKV) - log_{10} (Baseline htTKV)).

The 2-sided Type I error rate will be set at an alpha level of 0.05.

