3.9.3 Secondary Endpoint Analyses: Change from Baseline in eGFR

A secondary endpoint is the change from baseline in eGFR at months 12, 18, 24, and 30 days post-dose using the MDRD-4 formula (see Table 1).

For the 30 days post-dose endpoint, the change in eGFR from baseline to posttreatment follow-up is annualized (divided) by each subjects' treatment duration (in years). This normalization is necessary, otherwise the treatment group having more dropouts or earlier dropouts may bias the results.

At each timepoint (ie, months 12, 18, 24, and 30 days post-dose) and analysis of covariance (ANCOVA) model will be used to evaluate treatment effect. The ANCOVA model has eGFR as the dependent variable, treatment group as the factor, and baseline eGFR, patient age, and baseline htTKV as covariates.

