3.11 Subgroup Analyses

 Summary statistics and the ANCOVA analysis for htTKV described in Section 3.9.2 will be performed for each of the Mayo Classification groups (ie, Class 1A, 1B, 1C, 1D, and 1E). This will be done for the Month 12, 18, 24, and 30 days post-dose treatment visits.

The formulas for the Mayo classification groups are derived from the methods in Irazabel $(2015)^2$ and are presented in Section 3.15.

• Summary statistics and the ANCOVA analysis for eGFR described in Section 3.9.3 will be performed for each of the Mayo Classification groups (ie, Class 1A, 1B, 1C, 1D, and 1E). This will be done for the Month 12, 18, 24, and 30 days post-dose treatment visits.

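### SAP 3.10 and 3.11 compare htTKV at 30 days post-dose without allowing for time since baseline, although SAP 3.9.3 calls that allowance necessary for eGFR at the same visit

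*SAP*

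**What the plan says.** **Visit timing.** Protocol Table 2 (footnotes c and k) places the End-of-study visit 30 days (± 3) after the last dose and includes an MRI. Protocol 4.3 asks sites to try to obtain these procedures from subjects who withdraw.

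**htTKV at this visit.** SAP 3.10: "The htTKV at Months 18, 24, and 30 days post-dose will be analyzed in the manner as described in Section 3.9.2". In SAP 3.9.2, "The dependent variable is the log10 transformed change from baseline", and the model has treatment group and log10 baseline as its only terms. SAP 3.11 repeats this within each Mayo class: "This will be done for the Month 12, 18, 24, and 30 days post-dose treatment visits".

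**eGFR at this visit.** SAP 3.9.3 divides the change from baseline to follow-up by each subject's years of treatment and explains: "This normalization is necessary, otherwise the treatment group having more dropouts or earlier dropouts may bias the results". It then says: "The ANCOVA model has eGFR as the dependent variable, treatment group as the factor, and baseline eGFR, patient age, and baseline htTKV as covariates".

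**Slope model.** SAP 3.10.1 includes the 30-day MRI, and its time variable "is the time (in years) from baseline of the htTKV assessment".

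**Status.** The SAP lists 30-day htTKV among the supplementary and sensitivity analyses. The primary objective in both documents names it, and protocol 9.10 lists it as an additional efficacy endpoint, with ANCOVA as the efficacy method.

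**The concern.** Time from baseline to this MRI depends on when the subject stopped. The Efficacy Population requires at least 12 months of treatment and planned treatment is 24 months, so the MRI falls about 13 to 25 months after baseline. The sample size rationale assumes that kidneys grow on placebo, so a subject measured sooner shows less growth whatever the drug does. If one arm stops earlier or more often, it looks better.

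The SAP recognises this mechanism for eGFR and gives no reason why kidney volume would escape it. At stake is one supplementary comparison and its Mayo-class repeats. The undivided comparison could also disagree with the slope analysis through timing alone, and the SAP does not say which should be relied on.

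**Working it through.** **Inputs from the documents.** Placebo change 83.6 mL at 12 months, SD 90.0; tesevatinib change 26.4 mL; two-sided alpha 0.05 (SAP 3.1.2 and 3.9.2). 50 randomised and at least 40 completing per group (protocol synopsis), so at most 10 of 50 (20%) lost in each group.

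**Plan's own figure.** Difference 83.6 − 26.4 = 57.2 mL. With 40 per group the standard error is 90 × √(2/40) = 20.1 mL. Noncentral t power (78 df) is 80.2%, so the stated 80% reproduces.

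**Reference effect at this visit.** Carried linearly to Month 25: 57.2 × 25/12 = 119.2 mL.

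**Spurious difference with no drug effect.** Assume both arms grow at 83.6 mL/year. Then

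spurious difference = (gap between arms in the share of stoppers among those scanned) × (months lost) × 83.6/12.

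| Scenario (Efficacy Population) | Calculation | Spurious difference | Share of 119.2 mL | False-positive rate |
|---|---|---|---|---|
| 20% vs 0% stop at Month 12, all return | 0.20 × 12 × 83.6/12 | 16.7 mL | 14% | about 7-10% |
| 10% vs 0% stop at Month 18, all return | 0.10 × 6 × 83.6/12 | 4.2 mL | 3.5% | about 5% |
| Equal share and timing | 0 | 0 | 0 | about 5% |

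If only half the stoppers in the first row return, their share among those scanned is 0.20 × 0.5/(0.80 + 0.10) = 0.111. The difference falls to 0.111 × 83.6 = 9.3 mL, or 7.8%.

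On the log10 scale that the SAP uses, with assumed baselines of 750 to 2000 mL, a 20-point gap at Month 12 gives 13.7-13.9% of the projected effect, so the scale hardly matters.

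**False-positive rates.** These come from simulation on the mL scale without the baseline covariate, with 40 or 50 subjects per arm. Of the 12-month variance (90²), 25-100% was assigned to between-subject growth rates and the rest to measurement error. After dividing the change by time from baseline, the rate was 4.3-5.5%.

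**eGFR divisor (secondary).** The numerator runs to follow-up, while the divisor is treatment duration. Section 3.9.3 does not define that term, but the exposure formula in SAP 3.8 ends at the last dose. The overstatement per subject is (T + 30)/T: 760/730 = 1.041 at 24 months and 395/365 = 1.082 at 12 months. Between arms, with the same 20-point gap and an assumed decline of 2 to 5 mL/min/1.73 m²/year, the effect is 0.20 × (1.082 − 1.041) × 2 to 5 = about 0.02 to 0.04 mL/min/1.73 m²/year.

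**The case against.** **The slope model already handles timing.** This stands in large part: SAP 3.10.1 uses actual time and SAP 3.10.2 does the same for eGFR. What remains is that the SAP also plans the undivided comparison and does not rank the two.

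**The planned dropout allowance is symmetric.** This also stands. The documents allow for 10 losses in each group and forecast no imbalance. The 20% vs 0% case is the extreme within that allowance, not an expectation. Equal totals do not guarantee equal timing, however, and the SAP itself treats unequal dropout as a risk worth correcting for eGFR.

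**A stronger reading through mITT.** A reader might infer much larger errors there, because subjects who stop in the first months would enter. A 20-point gap at Month 3 gives 0.20 × 21 × 83.6/12 = 29.3 mL, or 24.6% of the projected effect. The documents do not clearly plan that analysis. SAP 3.9 allows mITT for supplemental work in general, but the bullet in SAP 3.10 reads "The primary and secondary efficacy endpoints will be performed on the mITT population", and the SAP classes 30-day htTKV as neither. Protocol 9.10 bases all efficacy analyses on the Efficacy Population.

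**Dropping the ANCOVA.** A reader might conclude that the slope model should simply replace it. That would remove an analysis that protocol 9.10 specifies for this endpoint.

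**Conclusion.** The inconsistency is real and minor. As written, the 30-day htTKV comparison can be biased by unequal stopping, for the reason that the SAP gives when it corrects eGFR. In the Efficacy Population the bias ranges from zero with equal dropout and timing to about 17 mL, with about 7-10% false positives, at the extreme of the planned allowance.

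These figures assume linear growth at the planned placebo rate in both arms, stoppers who grow like everyone else, and arm-specific stopping patterns that the documents do not give.

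It would be wrong to infer that the trial's main conclusion is at risk. The only formally controlled test (Month 12 htTKV), the sample size and the slope model are untouched. The eGFR divisor is a genuine mismatch of 4-8% per subject at 24 to 12 months of treatment, but it hardly moves the comparison between arms. Naming eGFR as the dependent variable straight after annualising its change is a wording gap; the annualised change is probably meant.

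**What to change.** 1. **SAP 3.10 and 3.11.** Keep the protocol 9.10 ANCOVA at the 30-day visit, but make its dependent variable the log10 htTKV change divided by years from the baseline MRI to the follow-up MRI. Show the undivided change as descriptive only. State that the SAP 3.10.1 slope difference governs interpretation, and which population applies.
2. **SAP 3.9.3 (secondary).** Divide the 30-day eGFR change by the time from the baseline to the follow-up measurement, and name that annualised change as the dependent variable at this visit.

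**Cost.** SAP wording and a little programming before unblinding; no new data. Dividing by time assumes roughly linear change. In the Efficacy Population, with 20% per arm stopping at Month 12, simulated power for 57.2 mL/year falls by at most 0.7 points (98.0% to 97.3%, with 75% of the 12-month variance from measurement error). If mITT were used with 20% per arm stopping at Month 3, unweighted annualising would cut power from 98.6% to 67.0% at the same error share, against 99.8% for the slope model. That is why the slope model should govern, especially in mITT.

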In summary, mild asymptomatic increases in amylase levels have been seen frequently in Study KD019-101, including in subjects in the 50 mg daily cohort, and appear to be due to increases in pancreatic amylase. Subjects with baseline elevations in amylase are no longer eligible for tesevatinib ADPKD studies. If amylase levels rise to 1.5 × ULN, evaluation of lipase, amylase isoenzymes, and lipid levels are performed (see Section 7.5.6).

Serum Creatinine Elevations

The initial data indicate that subjects with ADPKD receiving tesevatinib have experienced elevations of creatinine without elevations in cystatin C. The median changes from screening values for creatinine and cystatin C from all subjects receiving the 50 mg dose reveal that creatinine values were increased by 11.1% at Day 3, by 14.3% at Day 7, and increased by 10% at Day 28. Data after Day 28, including several subjects who have received tesevatinib for 24 months, do not indicate any significant ongoing change in creatinine. During the same time period, cystatin C levels did not change (median decreases were 0%, 1.9%, and 1.7% at Days 3, 7, and 28, respectively). Data from the 8 subjects enrolled into the 100 mg dose cohort, as well as subjects enrolled in subsequent cohorts, exhibited a similar pattern. This increase in creatinine occurs early and after approximately 7 days, does not continue to increase, similar to the increase in serum creatinine seen with cimetidine. Increases in creatinine were seen in previous clinical studies of tesevatinib; however, most of the previous studies were in subjects with malignancies, and in previous studies, cystatin C levels were not evaluated, so increases in serum creatinine that may not represent renal dysfunction were not recognized.

QTc Prolongation

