1.2.1.3. Clinical Pharmacokinetics

A preliminary noncompartmental analysis of tesevatinib pharmacokinetics (PK) from Phase 1 studies of intermittent dosing indicated that tesevatinib was rapidly absorbed following oral administration, with a median observed time to reach peak plasma concentration (T_{max}) of 4-8 hours. Area under the plasma drug concentration time curve (AUC) and the C_{max} generally increased approximately in proportion with dose over the full dose range (ie, 3.4 to 586 mg). Mean terminal half-life after 5 consecutive QD doses ranged from 50 to 92 hours, and appeared generally independent of dose. High inter-subject variability in exposure was observed with coefficient of variation (CV%) values of 46% and 43% for dose normalized C_{max} and AUC₀₋₂₄, respectively. Results from 5 subjects in the Phase 2 study who received 350 mg tesevatinib on the intermittent schedule showed that the concentration of tesevatinib appeared unchanged from cycle to cycle. These results suggest that tesevatinib does not accumulate significantly from one 14-day cycle to the next.

A preliminary noncompartmental PK analysis has been completed for 15 subjects given tesevatinib QD for at least 29 consecutive days. Tesevatinib was rapidly absorbed following oral administration (mean T_{max} ranged from 3.3 to 7.3 hours) and steady state appeared to have been reached by about Day 15. The estimated median accumulation ratio was 4.6 (accumulation ratio based on 300 mg QD dose). The median T_{max} at the MTD was 4 hours.

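### The supplementary eGFR slope model draws one straight line per arm through pre-dose, on-drug and off-drug values, so an early creatinine step on tesevatinib biases the slope difference by tenths of a unit per year, in a direction not known in advance

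*SAP*

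**What the plan says.** SAP 3.10.2 specifies the eGFR slope analysis by reference: "The MMRM model will be the same as the model described in Section 3.10.1". That model has an intercept and a linear time slope for each arm, plus a random intercept and random slope for each subject. The test is on β4, the difference in slopes. On the data to be used, 3.10.2 says: "The model will include the baseline and all post-baseline eGFR assessments". By SAP 2.4.2, creatinine is measured at Screening, Days 1, 14 and 28, monthly to Month 12, every two months to Month 24, and 30 days after the last dose. The model has no on-drug indicator, acute-phase term or change point.

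The protocol's account of Study KD019-101 (section 1.2, Serum Creatinine Elevations) describes the course on the 50 mg dose used here: "creatinine values were increased by 11.1% at Day 3, by 14.3% at Day 7, and increased by 10% at Day 28". It adds: "This increase in creatinine occurs early and after approximately 7 days, does not continue to increase". Later data, including several subjects treated for 24 months, "do not indicate any significant ongoing change in creatinine". On the other marker: "During the same time period, cystatin C levels did not change". The text likens the pattern to that of cimetidine. It also says of earlier tesevatinib studies, where cystatin C was not measured, that "increases in serum creatinine that may not represent renal dysfunction were not recognized".

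**The concern.** The sponsor's own data predict a step followed by a plateau in the tesevatinib arm, possibly with a return after the drug is stopped. The model allows only a straight line. Whatever part of the step the group intercept does not absorb goes into the slope. β4 can then differ from zero when the drug has no effect on progression, and it may be read as renal benefit or harm.

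eGFR is a stated secondary objective, and this is its only longitudinal analysis. The issue is the time structure of the slope model. It remains even if each by-visit comparison in SAP 3.9.3 is sound.

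**Working it through.** **The plan's own figures.** The documents give no effect, SD or power for the eGFR slope, so there is nothing to reproduce on this point. The one stated power figure, about 80% for htTKV with 40 per group, does reproduce: a difference of 83.6 - 26.4 = 57.2 mL with SD 90.0 gives 0.802 by the noncentral t. It does not bear on the slope.

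**Inputs from the documents.** Creatinine rise of 10% (Day 28) to 14.3% (Day 7); MDRD-4 exponent -1.154 (SAP Table 1); the visit schedule above; eGFR 30 to 80 in the design section (the inclusion criteria say 25 to 90).

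**Assumptions.** Baseline eGFR 55, the midpoint of 30 to 80; a constant step from the first post-baseline visit; equal true progression in both arms; calendar months.

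**Size of the step.**
- 1.10^-1.154 = 0.896, so D = 55 × 0.104 = 5.73.
- 1.143^-1.154 = 0.857, so D = 55 × 0.143 = 7.86.

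**Expected β4, 24-month completers.** There are 21 values: 1 baseline, 19 on drug and 1 off drug. With identical visits for every subject and the same terms in the fixed and random parts, the mixed-model estimate equals ordinary least squares. The assumed variances therefore drop out.

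Let r be the fraction of the step reversed at the post-dose visit. Relative to the on-drug plateau, the step pattern is D at baseline, 0 on drug and rD off drug, so

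β4 = D × [(t_first - t̄) + r(t_last - t̄)] / Σ(t - t̄)².

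With t in years, t̄ = 0.8626, t_last = 2.0821 and Σ(t - t̄)² = 8.753. This gives β4 = D × (-0.0985 + 0.1393r).

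Without the off-drug value, t̄ = 0.8016 and the sum of squares is 7.191, so β4 = -0.1115 × D.

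| Case | D = 5.73 | D = 7.86 | eGFR 30 to 80, rise 10 to 14.3% (D = 3.12 to 11.43) |
|---|---|---|---|
| Step fully reversed (r = 1) | +0.23 | +0.32 | +0.13 to +0.47 |
| Not reversed (r = 0) | -0.56 | -0.77 | -0.31 to -1.13 |
| Post-dose value missing | -0.64 | -0.88 | -0.35 to -1.27 |

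Units are mL/min/1.73 m² per year, and a positive value favours tesevatinib. β4 is zero at r = 0.0985/0.1393 = 0.71. When r = 1, the group intercept takes about -5.4 of the -5.73.

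**Sensitivity at the 10% step.**
- Day 14 still at the 14.3% rise, 10% afterwards: +0.43 (reversed), -0.36 (not reversed).
- 50 per group, 20% stopping in equal numbers at Months 3, 6, 12 and 18, with every stopper attending the post-dose visit; assumed intercept SD 15, slope SD 1 to 4, residual SD 2.5 to 6: +0.24 to +0.28 (reversed), -0.61 to -0.82 (not reversed).
- Rejection rate at nominal 0.05, 40 completers per group, same slope and residual SDs: 0.056 to 0.126 (reversed), 0.087 to 0.487 (not reversed).
- REML simulation, 150 runs per case, slope SD 2, residual SD 4: mean β4 +0.23 with 8.7% rejections, and -0.56 with 19%.

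**Check of the remedy.** A constant plateau from Day 28 has slope zero, so a fit to on-drug values alone gives β4 = 0, with or without dropout. If the step is proportional, on-drug eGFR is 0.896 of its true value, and a raw-scale slope is too shallow by 0.104 times the true decline: +0.21, +0.31 or +0.52 for declines of 2, 3 or 5 per year. On the log scale a proportional step is an additive constant, and the slope difference is zero.

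**An alternative that is not equivalent.** Keeping all data and adding an on-drug term for the tesevatinib arm gives zero if r = 1, but -0.69 per year if r = 0 (10% step).

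**The case against.** The strongest reply is that the plan has other safeguards and that little depends on this model. SAP 3.9.3 analyses eGFR change from the pre-dose baseline to 30 days after the last dose. If the step reverses, that contrast is free of it. Cystatin C is measured and summarized by arm and visit (Protocol 9.11, SAP 3.13.2). SAP 3.10 labels the slope supplementary, and 3.12 leaves even the secondary eGFR endpoints without multiplicity control. All of this stands and limits the weight of the point. A reader might infer that the slope is the only planned analysis able to separate an early creatinine shift from progression, and the documents do not support that. These checks are partial, however, and none changes what β4 estimates.

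A reader might also infer a built-in spurious benefit, because the drug should have left the body by the post-dose visit: "Mean terminal half-life after 5 consecutive QD doses ranged from 50 to 92 hours", so 720 hours is about 8 to 14 half-lives. But the protocol reports no creatinine values after stopping. Reversal is an inference from the half-life and the likeness to cimetidine. Without it the bias goes against tesevatinib, and near 71% reversal it vanishes.

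Third, one might expect early stopping to produce a large bias. The dropout results show only a modest shift when stoppers attend the post-dose visit. Non-reversal and missed post-dose visits matter more. Finally, the protocol calls the creatinine findings initial data; they are medians from a study without a control group.

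**Conclusion.** The point holds as a limited one. As specified, β4 in SAP 3.10.2 does not isolate progression if the creatinine step reported at 50 mg recurs. For completers at an assumed eGFR of 55, the bias runs from about +0.2 to -0.6 per year with a 10% step and reaches about -0.9 with a 14.3% step and no post-dose value. Its sign depends on off-drug recovery, which the documents do not report, and on attendance at one visit. The inflation of the false-positive rate is small if the step fully reverses and slopes vary widely between subjects; it can be substantial if the step persists.

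The completer figures rest on the assumed baseline eGFR and a constant step, not on variance assumptions. The dropout figures and rejection rates also depend on the assumed SDs. The documents do not support a claim of bias in a fixed direction or any effect on the primary htTKV result. The change should be made because it is cheap and the shape it guards against is in the sponsor's own data.

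**What to change.** In SAP 3.10.2, estimate the slope from on-treatment eGFR values from Day 28 to the last on-drug visit. Enter baseline eGFR as a covariate rather than as a response, and leave the post-dose value to its own analysis in 3.9.3. Fit the model on log eGFR, or repeat it with the cystatin C already collected, because the raw scale keeps about +0.2 to +0.5 per year if the step is proportional. Do not offer an on-drug indicator as an equivalent: it is unbiased only if the step fully reverses. The all-data model can stay as a labelled sensitivity analysis, with a note that its slope mixes the step with progression.

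The cost is SAP wording and a small code change; no new data are needed. The downside should be stated in the SAP: this is an on-treatment slope over a slightly shorter span, and subjects who stop early contribute little to it.
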